#### L.3.3.2 Subject accountability

Subjects already enrolled and willing to extend their follow-up from 12 to 60 months are to be re-consented. Re-consenting is to occur at or prior to the 12-month follow-up visit. Enrolled subjects who decline to continue to participate in follow-up beyond 12-months shall exit the study upon the completion of their 12-month visit.

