#### L.3.5.2 Data collection requirements

The data collection schedule is summarized in Table L-2. Imaging source data is to be sent to a core lab for analysis up to the 12-month follow-up visit. Imaging source data beyond 12-months post-index procedure is not to be sent to the core lab for analysis. Instead, study sites are to report the results of the imaging performed as standard of care and in line with local and site

requirements directly on the e-CRF. Routinely acquired images may be required for adjudication purposes in case of CEC adjudication or any other safety event.

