Subjects will be followed until the last subject enrolled has completed the 1 year follow-up visit or until PMA approval is obtained in the US (whatever is later), however, Medtronic will work with FDA to determine if longer term follow after PMA approval is required. A post-approval analysis of 1-year Major Device Event (MDE) rate is planned.

6. Determination of Sample Size

One hundred (100) enrolled subjects will ensure 87 evaluable subjects at 30 days. The primary endpoint analysis will be completed upon 87 evaluable subjects reaching the 30 day endpoint. Based on Valor II study results, Valiant Evo is expected to perform similarly and have 6% of MDE combined with access and/or deployment failures at 30 days. The sample size of 87 evaluable subjects will provide 85% statistical power for the study hypothesis. The type I error is controlled at the one-sided 0.025 level.

Table 1: Power Analysis

True rate of MDEs combined with access and/or deployment failures at 30 day with Valiant Evo	6%
Performance Goal	16%
Significance level	0.025
Statistical test	One-sided binomial test
Evaluable sample size	n=87
Enrollment	Minimum of 100 subjects enrolled to ensure 87 evaluable subjects
Statistical power from the 87 evaluable subjects	85%

One hundred (100) enrolled subjects will also ensure 63 evaluable subjects at 1-year on MDE rate for the post-approval analysis. The VALOR II study with the Valiant stent graft system enrolled 160 patients with DTAA and was assessed through 12 months for purposes of PMA (P100040) approval. Through 1-year post-

treatment, the rate of MDEs combined with access and/or deployment failures was 7.1% (11/153) (Medtronic internal data using the Valiant Evo proposed definition). Therefore, for the purpose of post approval analysis, the rate of MDEs combined with access and deployment failures at 1-year with Valiant Evo is estimated to be 7.1% (refer to Table 22 below for power analysis assumptions).

Table 2: Power Analysis for Post-approval Analysis of 1-year Endpoint

Estimated rate of MDEs combined with access and/or deployment failures at 1 year with Valiant Evo	7.1%
Performance Goal (PG) at 1-year	20%
Significance level	0.05
Statistical test	One-sided binomial test
Evaluable sample size	N = 63 at 1 year
Enrollment	IDE cohort will enroll a minimum of 100 subjects and is expected to have a minimum of 63 evaluable subjects at 1-year follow up.

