- Aneurysm-Related Mortality within 365 days
- MDEs within 365 days
- All AEs within 365 days including:
 - MAEs
 - SAEs
- Secondary procedures within 365 days
- Loss of stent graft patency within 12 months based on imaging findings
- Endoleaks at 12 months based on imaging findings
- Stent graft migration at 12 months as compared to 1-month imaging
- Aneurysm expansion > 5mm at 12 months based on imaging findings relative to the 1-month visit

Secondary endpoints are to be assessed beyond 12 months. The following secondary endpoints are to be evaluated at 24, 36, 48, and 60 months:

- All-cause mortality
- Aneurysm-Related Mortality
- MDEs
- All AEs and SAEs
- Secondary procedures
- Loss of stent graft patency based on site reported imaging findings
- Endoleaks based on site reported imaging findings

- Stent graft migration as compared to 1-month imaging
- Aneurysm expansion > 5mm based on site reported imaging findings relative to the 1-month visit

Health-related quality of life outcomes are to be assessed at all scheduled follow-up visits using the EQ-5D questionnaire.

Stent graft migration will be determined by the core lab or site imaging case report from (CRF). Core lab assessment and site reported result will be analyzed separately. Aneurysm expansion will be calculated. When 1-month image is not available, the latest image taken prior to 1-month will be used for calculation.

Descriptive statistical analyses will be performed on secondary endpoints. No inferential statistical analysis is planned for secondary endpoints.

Non-image endpoints event rates such as mortality, secondary procedures, MAEs, SAEs, conversion to open surgery, and thoracic aortic aneurysm ruptures through 1 year will be calculated in the same way as the MDE rate, specified in Table 5. The event rates beyond 1 year through 5 years will be analyzed using Kaplan Meier method.

Imaging based Event Rate Calculation:

Unless otherwise specified, imaging assessment will be performed by site as well as the core lab. Assessments from the core lab will be the primary result for the PMA and PMA-s submissions and analyzed separately from those by site. Imaging based event rate will be calculated using statistical analysis windows as follows (Table 6):

Table 6: Imaging based Event Rate Calculation:

Event rate = m/n	At 1 Month	At 6 Months	At 12 Months

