m = No. of Subjects Who Had Event(s)	No. of subjects who had an event with scan day within the 1-month window.	No. of subjects who had an event with scan day within the 6-month window.	No. of subjects who had an event with scan day within the 12-month window.
n = No. of Subjects Who Had Readable Images	No. of subjects who had a readable image within the 1-month window.	No. of subjects who had a readable image within the 6-month window.	No. of subjects who had a readable image within the 12-month window.
Event rate = m/n	Through 1 Month	Through 6 Months	Through 12 Months
m = No. of Subjects Who Had Event(s)	No. of subjects who had an event with scan day within the 1-month window.	No. of subjects who had an event with scan day within 1- or 6-month windows.	No. of subjects who had an event with scan day within 1-, 6- or 12-month windows.
n = No. of Subjects Who Had Readable Images	No. of subjects who had a readable image within the 1-month window.	No. of subjects who had an event (counted in m) or had a readable image within the 6-month window.	No. of subjects who had an event (counted in m) or had a readable image within the 12-month window.

The imaging based event rates by visit at 24, 36, 48 and 60 months will be calculated in a similar way as above; i.e., m = number of subjects who had an event with scan day within the statistical analysis window of the specific time point; n = number of subjects who had a readable image within the 12-month window.

The cumulative event rate through 24, 36, 48 and 60 months will be estimated using survival analysis. Kaplan-Meier estimates, along with its standard error using the Greenwood method, will be reported for non-image based events. The image-based events are interval censored data and the interval censored survival analysis method will be used to calculate the event rates.

When reporting the site reported endoleaks, both site imaging findings and the events treated during secondary procedures will be accounted for in the analysis.

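### By-visit imaging rates at 24 to 60 months divide that visit's events by the number imaged at 12 months, so they are too low whenever fewer subjects are imaged late

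*SAP*

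**What the plan says.** SAP section 7.9, under the imaging-based event rate calculation, first sets out Table 6. For each *At* rate (1, 6 and 12 months), the table counts events and readable images in the same visit's window.

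The text below the table extends this to 24, 36, 48 and 60 months and says the calculation is similar. It then spells out the two terms:

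- numerator: "m = number of subjects who had an event with scan day within the statistical analysis window of the specific time point"
- denominator: "n = number of subjects who had a readable image within the 12-month window"

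Cumulative late imaging rates are handled separately: "The image-based events are interval censored data and the interval censored survival analysis method will be used to calculate the event rates". On the status of these endpoints the SAP states: "No inferential statistical analysis is planned for secondary endpoints".

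Three other places bear on how many subjects will be imaged late:

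- Protocol L.3.3.2, for the International cohort: "Enrolled subjects who decline to continue to participate in follow-up beyond 12-months shall exit the study upon the completion of their 12-month visit".
- Protocol L.3.5.2, on imaging beyond 12 months: "study sites are to report the results of the imaging performed as standard of care".
- SAP section 5, for the US cohort: "Medtronic will work with FDA to determine if longer term follow after PMA approval is required".

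**The concern.** A by-visit rate should be a proportion of the subjects assessed at that visit. Here the numerator and denominator come from different sets of subjects:

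- A subject imaged at 12 months but not at 36 months stays in the 36-month denominator with no chance of entering the numerator. In effect the subject is counted as event-free.
- A subject with a 36-month event but no readable 12-month image enters the numerator and not the denominator. The ratio is then not a proportion of any defined group.

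The first effect grows as follow-up thins out, and it favours the device. Endoleak, migration, loss of patency and aneurysm expansion at 24 to 60 months are named secondary endpoints. Protocol L.3.2 gives longer-term safety and effectiveness as the reason for extending follow-up. A fixed 12-month denominator could show a falling rate over years 2 to 5 when the rate among imaged subjects has not changed.

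**Working it through.** **Windows (SAP Table 3).** 12 months is days 305–548. The late windows are days 549–913 (24 months), 914–1278 (36), 1279–1643 (48) and 1644–2009 (60). None overlaps the 12-month window, so a 12-month image cannot also serve as the late image.

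**Algebra.** Let m_t be the subjects with an event in the late window, N_late those with a readable image in that window, and N12 those with a readable image in the 12-month window.

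- Rate as the SAP defines it: m_t / N12
- Visit-matched rate, following the *At* columns of Table 6: m_t / N_late
- Ratio of the first to the second: N_late / N12

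The relative understatement is 1 − N_late/N12, whatever the true rate. It is zero if N_late = N12. If N_late > N12, the SAP rate is too high. If m_t = 0, both rates are 0%.

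**Numbers.** The documents state no late imaging count or rate, so there is no figure of the plan's own to reproduce. For illustration, N12 = 63 is borrowed from SAP Table 2. That is the planned minimum evaluable for the 1-year MDE rate, not an imaging count. The late counts are assumed. With a true rate of 10% among those imaged:

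| N_late (assumed) | N_late/63 | Reported rate | Relative understatement |
|---|---|---|---|
| 63 | 1.000 | 10.0% | 0% |
| 57 | 0.905 | 9.0% | 10% |
| 50 | 0.794 | 7.9% | 21% |
| 38 | 0.603 | 6.0% | 40% |
| 32 | 0.508 | 5.1% | 49% |

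In counts, 5 events among 50 imaged is 5/50 = 10.0% (exact 95% CI 3.3% to 21.8%). The SAP's definition gives 5/63 = 7.9% (2.6% to 17.6%).

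**A lesser, separate point in Table 6.** The *Through 6 Months* denominator is "No. of subjects who had an event (counted in m) or had a readable image within the 6-month window". It keeps every subject with an event, but an event-free subject only if there is a readable 6-month image. SAP section 5 says the 6-month visit is not mandatory for International subjects. Among the listed 6-month endpoints this chiefly touches loss of patency.

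For illustration, assume 53 US and 47 International subjects (100 in total), all events seen at 1 month, and 6-month images for 90% of event-free US subjects and a fraction f of event-free International subjects. With true rate r:

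- m = 100r
- n = m + (1 − r)(53 × 0.9) + (1 − r)(47f)

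For r = 1% and f = 0.1: n = 1 + 47.2 + 4.7 = 52.9, so the reported rate is 1/52.9 = 1.9%. At f = 0.7 it is 1.2%. For r = 2%, the reported rate is 3.8% at f = 0.1 and 2.5% at f = 0.7.

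**The case against.** The strongest reply is that this is a drafting slip. The sentence calls the rates by-visit, says they follow Table 6, and ties the numerator to the specific time point, so a careful reader can work out what was meant. That is probably how the clause arose. It does not remove the problem: SAP section 3 describes the document as a guideline for the biostatistician and programmers, and the explicit formula is what they would code and validate against. Nothing elsewhere in either document corrects it.

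A second reply is that late attrition may be modest. Protocol Tables L-1 and L-2 schedule 24- to 60-month visits with contrast CT or MRI, and SAP section 5 lists the same visits as required for US subjects. This stands as far as it goes: the documents make fewer late images likely, through refusal of the extension, deaths and missed scans, but give no basis for the amount. Only the factor N_late/N12 is firm.

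A third reply is that the outputs are descriptive and the cumulative estimates are sound. Both are true, and they limit the severity. The by-visit rates are still reported in their own right.

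On the *Through 6 Months* point, placing all events at 1 month is the worst case, and requiring known status is a recognised convention. If 6-month scanning is unrelated to outcome, the bias is upward or nil, but its size is an illustration. *Through 12 Months* has the same structure, but the 12-month visit is required in both cohorts, so the asymmetry should matter less there.

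**Conclusion.** The concern holds. As written, the late by-visit imaging rates equal the visit-matched rates times N_late/N12, and their numerators need not be subsets of their denominators. They are understated whenever fewer subjects have a readable image at the late visit than at 12 months and at least one event is seen.

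With N12 = 63 and 57 to 32 subjects imaged late (both assumed), the understatement runs from about 10% to 49% in relative terms.

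The effect is confined to descriptive secondary endpoints: endoleak, migration, patency loss and expansion by visit at 24, 36, 48 and 60 months. The 30-day primary test, the 1-year MDE analysis, the *At* imaging rates through 12 months and the interval-censored cumulative rates do not use this denominator. It should be fixed before the late outputs are programmed, but it does not threaten the trial's main conclusions.

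**What to change.** In the sentence below Table 6, define n as the number of subjects with a readable image in the analysis window of the visit being reported, the same window that defines m.

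The cost is SAP wording and programming; no new data are needed. The late rates will be somewhat higher and their intervals wider, as in the 5/50 against 5/63 example.

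Optionally, for loss of patency within 6 months, the interval-censored method the SAP already plans for later cumulative imaging rates could be used. The by-visit 6-month rates and the *Through 12 Months* rates need no change.

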### C.7 Sample size

A sample of 47 subjects will be included and analyzed to support CE marking. The sample size of 47 subjects is considered adequate to assess the primary endpoint, which is defined as the proportion of subjects who experienced access/deployment failure or MDE within 30-days post index procedure.

Based upon the reported events from the VALOR II study on the Valiant Xcelerant stent graft system, the primary endpoint defined by this protocol would have a failure rate of 5.6% (9/160) within 30 days post index procedure. Considering the failure rate of Valor II, it is expected that Valiant Evo would perform similarly, meaning that 3 out of 47 subjects (6.4%) would likely fail within 30 days of implantation. The precision of this assumed 6.4% point estimate can be assessed by calculating the distance from the calculated 1-sided 95% upper confidence limit. This distance, or margin of error, is calculated to be <10% for this trial; therefore, considered adequate to assess the primary endpoint.

Due to sampling variation, different number of MDEs, anywhere from 0 to 47, might be observed, which would result in different confidence intervals depending on the outcomes as shown in Table C-1.

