**Table C-1: Sampling Variation and Its Impact to Study Results**

Observed number of events (k)	Observed event rate	Probability to observe k events	Probability to observe k or less events	One-sided 95% Upper Confidence Limit	Two-sided 95% Confidence Interval
0	0%	0.0666	0.0666	6.2%	[0%, 7.5%]
1	2.1%	0.1858	0.2524	9.7%	[0.1%, 11.3%]
2	4.3%	0.2535	0.5059	12.8%	[0.5%, 14.5%]
3	6.4%	0.2256	0.7314	15.7%	[1.3%, 17.5%]
4	8.5%	0.1472	0.8786	18.4%	[2.4%, 20.4%]
5	10.6%	0.0751	0.9537	21.1%	[3.5%, 23.1%]
6	12.8%	0.0312	0.9849	23.6%	[4.8%, 25.7%]
7	14.9%	0.0108	0.9957	26.2%	[6.2%, 28.3%]

8	17.0%	0.0032	0.9989	28.6%	[7.6%, 30.8%]
9	19.1%	0.0008	0.9998	31.0%	[9.1%, 33.3%]
10	21.3%	0.0002	1.0000	33.4%	[10.7%, 35.7%]

Note: Only 0 to 10 events are tabulated as probability of observing larger number of events is decreasing quickly. Probabilities were calculated based on the 5.6% MDE rate in the target population. An exact method (Clopper-Pearson) was used in calculating confidence interval, the same method to be used for data analysis.

Table C-1 also shows that the probability of observing 3 or less events in a 47-subject sample is 0.7314. The probability of observing 6 or more events is 0.0463 (=1 – probability of 5 or less). Based on this, the expectation is to see less than 6 events in this trial provided that the Valiant Evo performs similarly to its predicate.

Given the sample size of 47 subjects, the confidence interval estimate provides limited but desired precision of a statistical estimation or control of sampling variation (C.I. width) as shown.

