**Table H-1: Time Windows for Statistical Analyses**

Study Visit	Target Day	Time Window
Implant	0 days	Day 0
1 Month	30 days	1 – 90 days
12 Months	365	305 – 548 Days

If there are two or more assessments in the same time window, then the assessment closest to the target day will be used in the analysis of event rate at a given time point. In addition to endpoints, summaries of subject disposition, demographics, baseline characteristics, and subject accountability will be provided.

Subset analysis will be performed by-sex separately for the primary endpoint descriptively and reviewed for clinical significant difference.

All analysis will be performed on the modified intent-to-treat analysis set, which includes all included subjects. Subjects will be considered as included in the study as described in section F.1.

During statistical analysis, imputation of missing data will not be performed except for data related to the onset date of an adverse event or a death. In cases where the onset date of an event or a death is incomplete and unresolvable via data query, the 15th day of the known month or July 1st of the known year will be used.

Statistical analyses for this study will be performed using the Statistical Analysis System (SAS) for Windows (Version 9.1 or higher) or other widely-accepted statistical or graphical software.

Analysis for the Regulatory Submission:

For the primary endpoint, which is defined as the proportion of subjects experiencing an MDE within 30 days post-implantation, a 1-sided 95% confidence interval using the exact method (Clopper-Pearson) will be constructed in addition to event count frequency.

Additionally, a two-sided 95% confidence interval will also be provided. The SAS procedure PROC FREQ will be used for calculation of the confidence interval.

The analysis for the regulatory submission will take place when the first 47 subjects have been implanted with the study device for at least 30 days except that a subject expires early. Endpoints will be analyzed for these 47 included subjects as defined in Section C.2.

Interim Analysis:

No interim analysis is planned prior to the CE Mark Submission.

Annual Report:

An annual report will be provided for all enrolled subjects at the time of reporting according to requirements from notified bodies in the European Union and regulatory agencies in various countries.

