7.10. Safety Evaluation

All adverse events (AE) will be coded using the Medical Dictionary for Regulatory Activities (MedDRA) and categorized by System Organ Class (SOC) and Preferred Term (PT) for summary. Device-related AEs, procedure-related AEs, and serious AEs will be tabulated separately and by time period. The denominator in event rate calculation will be based on the number subjects available at the beginning of each time period. The relationship to device and procedure as well as seriousness will be based on site-reported data from the AE case report form (CRF).

The survival from all-cause mortality and aneurysm-related mortality over one year time or longer will be described by the Kaplan-Meier survival curve and the associated Kaplan-Meier estimate will be calculated along with its standard error using the Greenwood method.

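### For a rare non-image outcome with no events, the only precision measure the SAP names for Kaplan-Meier rates, the Greenwood standard error, is exactly 0 however few subjects were followed

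*SAP*

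**What the plan says.** SAP 7.9 splits non-image event rates at 1 year. Up to 1 year they are crude proportions: "conversion to open surgery, and thoracic aortic aneurysm ruptures through 1 year will be calculated in the same way as the MDE rate" (Table 5). After that, "The event rates beyond 1 year through 5 years will be analyzed using Kaplan Meier method". For the cumulative rates through 24, 36, 48 and 60 months, the reporting rule is "Kaplan-Meier estimates, along with its standard error using the Greenwood method, will be reported for non-image based events".

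SAP 7.10 covers all-cause and aneurysm-related mortality at one year or longer and repeats the rule: "the associated Kaplan-Meier estimate will be calculated along with its standard error using the Greenwood method". Protocol H.1 has a matching sentence, but for all-cause mortality only.

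Neither document names a confidence interval, a transformation, a rule for zero events or a display of numbers at risk for any Kaplan-Meier estimate. The intervals that are planned belong to the protocol's primary endpoint. There the protocol sets a one-sided exact limit and adds that "a two-sided 95% confidence interval will also be provided".

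**The concern.** The Greenwood variance is a sum over event times. With no events there is nothing to sum, so the standard error is 0. A table built to the SAP's rule would then show a 0.0% rate with a standard error of 0.0%, the same for 20 subjects as for 100. Read as an error bar, that says the rate is known to be zero.

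The outcomes most exposed are rare and matter for durability: aneurysm-related death, and rupture or conversion if they are shown separately beyond 1 year. Protocol L.3.2 gives long-term safety and effectiveness as the reason for extending follow-up to 60 months. The number followed will also fall. SAP 6 counts on only 63 evaluable subjects of 100 at 1 year, and under Protocol L.3.3.2 subjects who decline re-consent leave after the 12-month visit. The information about a zero count therefore shrinks over time, while the reported standard error stays at 0.

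**Working it through.** **Inputs.** Pooled enrolment is 100, with 63 evaluable at 1 year (SAP 6). For the International trial, "A sample of 47 subjects will be included and analyzed to support CE marking" (Protocol C.7). The value n = 30 is my illustration of late follow-up; the documents give no number for 48 or 60 months. They also give no rate for rupture, conversion or aneurysm-related death taken singly, so I use assumed cumulative rates of 0.5% to 3%.

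**1. The plan's own zero-event figure.** The note to Table C-1 says: "An exact method (Clopper-Pearson) was used in calculating confidence interval, the same method to be used for data analysis". With 0 events in n, the exact upper limit is 1 − a^(1/n), where a is the tail probability.
- One-sided 95%: 1 − 0.05^(1/47) = 6.2%
- Two-sided 95%: 1 − 0.025^(1/47) = 7.5%

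Both match the zero-event row of Table C-1.

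**2. Greenwood standard error.** SE = S(t) × √[ Σ dᵢ / (nᵢ(nᵢ − dᵢ)) ], summed over event times up to t, where dᵢ is the number of events and nᵢ the number at risk. With no events the sum is empty, S(t) = 1 and SE = 0. A numerical check gave 0 at n = 100, 87, 63, 47, 30 and 20 with full follow-up, and at n = 100 with staggered censoring.

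**3. What zero events actually supports.** Two-sided 95% upper limit, 1 − 0.025^(1/n), if all n subjects are followed to the time point:

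| n | Greenwood SE | Exact upper limit |
|---|---|---|
| 100 | 0 | 3.6% |
| 63 | 0 | 5.7% |
| 30 (illustrative) | 0 | 11.6% |

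With censoring, the effective n lies somewhere between the number still at risk and the number enrolled.

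**4. How likely is a zero count?** P(no event) = (1 − p)^100 for 100 fully followed subjects:

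| Assumed p | P(no event) |
|---|---|
| 0.5% | 61% |
| 1% | 37% |
| 2% | 13% |
| 3% | 5% |

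**5. Where it is unlikely.** For MDEs combined with access or deployment failure, SAP 6 assumes 7.1% at 1 year: (1 − 0.071)^100 ≈ 0.0006. The rate for MDEs without those failures is not given and would be somewhat lower. All-cause mortality has no planning rate, but at an assumed cumulative 5% the chance of no death in 100 is already only 0.6%.

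**The case against.** The best defence is that these are descriptive endpoints: "No inferential statistical analysis is planned for secondary endpoints". No test, performance goal or decision uses a Kaplan-Meier standard error, and SAP 3 calls its methods flexible. That is true and keeps the point small. It does not remove the point, because an interval states precision and is not a test. The protocol itself is not hypothesis driven, yet it plans exact intervals for its descriptive primary endpoint.

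The defence is also right to limit the scope. A reader might infer more than the documents support in four ways:
- **That intervals are excluded.** The SAP names none, but forbids none.
- **That limits below 0% would be reported.** One event in 100 gives an estimate ± 1.96 SE of −0.95% to 2.95%, against exact limits of 0.03% to 5.45%. Neither document plans that interval.
- **That rupture and conversion are affected throughout.** Through 1 year they are crude proportions. The 24- to 60-month lists contain them only as MDE components, so a separate Kaplan-Meier result is one reading of SAP 7.9. Because the curve is cumulative, a single event at any time since Day 0 makes the standard error non-zero.
- **That Protocol H.1 or device-related adverse events share the problem.** H.1 applies Kaplan-Meier to all-cause mortality only. SAP 7.10 tabulates device-related adverse events by period, using the subjects available at the start of each.

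A last objection concerns the remedy. An exact limit on the number still at risk discards the event-free time of subjects censored earlier and so overstates the uncertainty. That stands, and the fix has to say so.

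**Conclusion.** The point holds within a narrow scope. For a rare non-image outcome reported by Kaplan-Meier with no event since Day 0, following SAP 7.9 and 7.10 as written gives a standard error of 0, where the data allow a true rate of up to 3.6% (100 followed), 5.7% (63) or 11.6% (30, illustrative). Those limits assume complete follow-up of the stated number. Whether a zero count arises depends on rates that the documents do not give; at 1% to 2% the chance is 37% to 13% in 100 fully followed subjects.

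The primary test, its power and its type I error are untouched. This is a weakness in how late secondary results would be reported, not a design error, and its importance is low.

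**What to change.** In SAP 7.9 and 7.10:
- Report Kaplan-Meier estimates with 95% limits from the complementary log-log transformation, and the number at risk at 12, 24, 36, 48 and 60 months. The Greenwood standard error can stay as an extra column.
- When no event has occurred, the log-log limits are undefined. Show an exact upper limit in place of SE = 0 and state its denominator. If that is the number still at risk, label the limit as conservative, because it ignores the event-free follow-up of censored subjects.

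The cost is a short addition to the text and a standard option in the survival procedure. The one real decision is which denominator to use for the zero-event limit, and it should be made before the data are seen. No new data are needed. The downside is that zero-event results will look less certain.
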